13.1. Sample SAS Code

Sample SAS Code for MMRM analysis:

```
proc mixed data=indata;
class trt visit;
model chg /*or pchg*/ = base trt visit trt*visit/ ddfm=kr s;
repeated visit/type=UN subject=usubjid;
lsmeans trt*visit/pdiff cl alpha=0.1;
run;
```

Sample SAS Code for MMRM analysis with Fibrosis Status Y/N as factor:

```
proc mixed data=indata;
class trt visit biopsy_confirmed_NASH_yn;
model chg /*or pchg*/ = base trt visit biopsy_confirmed_NASH_yn trt*visit/
ddfm=kr s;
repeated visit/type=UN subject=usubjid;
lsmeans trt*visit/pdiff cl alpha=0.1;
run;
```

Sample SAS Code for Wilcoxon Rank Sum Non-Parametric analysis:

```
proc npar1way data=indata wilcoxon alpha=0.1;
class trt;
var chg /*or pchg*/;
exact wilcoxon;
run;
```

Sample SAS Code for Hedges-Lehman Estimation:

```
proc npar1way data=indata hl alpha=0.1;
class trt;
var chg /*or pchg*/;
exact hl;
run;
```

Sample SAS Code for Multiple Imputation Using Control Based Pattern-Mixture Model:

```
proc mi data = non_mono out=monotone niimpute=100 seed=123;
var trt01pn day50 day92;
mcmc chain = multiple impute=monotone;
run;
```

Note: Data needs to be in wide format for the multiple imputation procedure Also, dummy variables are need for categorical factors with more than two levels such as TREATMENT.

```
proc mi data=monotone out=imputed1 nimpute=1 seed = 124;
by _imputation_;
class trt01pn;
var trt01pn day50 day92;
monotone reg(/details);
mnar model (day50 day92/modelobs=( trt01pn ='0')) ;
run;
```

```
proc mixed data=imputed;
by _imputation_;
class subject trt visit;
model pchg = base trt visit trt *visit/ddfm=kr;
repeated visit / sub=subject type=un;
lsmeans trt *visit/pdiff cl;
ods output lsmeans=lsmeans diffs=diffs;
run;
proc sort data=lsmeans;
by trt visit _imputation;
run;
proc mianalyze parms=lsmeans;
modeleffects trt * visit;
ods output parameterestimates=lsm;
by trt visit;
run;
proc sort data=diffs;
by visit _imputation;
run;
proc mianalyze parms=diffs;
modeleffects trt * visit;
ods output parameterestimates=dif;
by visit;
run;
```

BIO89-100-002 (Part 2)
NCT #: NCT04048135

Page 1 of 41

Statistical Analysis Plan

[figure not shown]
Protocol BIO89-100-002 (Part 2, Single Cohort)

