8.4. Statistical Analyses

The statistical analysis plan (SAP) will be developed and finalized before database lock and will describe the subject populations to be included in the analyses, and procedures for accounting for missing, unused, and spurious data. Pooling of placebo subjects in Part 1 will be performed when applicable and will be specified in the analysis plan. This section is a summary of the planned

statistical analyses of the primary and secondary endpoints. Analysis of biomarkers and PD endpoints as well as their correlation with PK will be detailed in the SAP.

In general, summary descriptive statistics will be presented for demographics and baseline characteristics, safety endpoints, PK, and PD parameters. Descriptive statistics will include number of observations, mean, standard deviation, median, minimum, and maximum for continuous parameters. For PK and PD parameters, descriptive statistics will include the number of observations, arithmetic and geometric means, standard deviation, coefficient of variation, median, minimum, and maximum. Categorical parameters will be displayed using counts and percentages within each category.

For Part 1, while no formal hypothesis testing is planned for the primary objectives, the evaluation of potential efficacy will be determined based on the totality and pattern of data from the biomarker and PD endpoints. The assessment of biomarker and PD endpoints will employ 90% confidence intervals and significance testing for assessing within group changes and percentage changes from baseline and comparisons of the BIO89-100 doses to the pooled placebo group. Details will be provided in the SAP.

The correlation between relevant PK parameters and PD endpoints will be examined as will be detailed in the SAP.

Subjects with dose interruptions impacted by the COVID-19 pandemic will be noted in the listings. Subgroups including and excluding subjects with dose interruptions due to COVID-19 pandemic may be considered for both efficacy and safety analyses as appropriate.

For Part 2, endpoints of different histological responses will be summarized with the point estimates and 95% confidence intervals of the proportions of subjects who meet the response criteria using the biopsy analysis set.

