3.5. Sample Size and Power

No formal sample size calculation was performed for the primary endpoint(s) as the total of approximately 83 subjects, consisting of 6:2 (Cohort 1), 12:3 (Cohort 2), 9:3 (Cohorts 4 and 6) or 14:4 (Cohorts 3 and 5) receiving active: placebo, respectively is considered adequate to inform on the endpoints for this Phase 1b study.

A power assessment based on magnetic resonance imaging – proton density fat fraction (MRI-PDFF) endpoint (percent change from baseline to End of Treatment in liver fat content, an important biomarker) shows that 9, 12 and 14 subjects in a dose cohort compared to the pooled 19 placebo subjects will provide [REDACTED] power, respectively, to detect a difference in mean percentage change from baseline between treatment groups of [REDACTED], assuming

a standard deviation of █ in each group. Calculation was based on two-sample one-sided t-test with alpha at 0.05 (e.g., two-sided alpha at 0.10).

Subjects who withdraw from the study before the Day 50 assessments may be replaced at the discretion of the Sponsor.

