5.10. Definition of Randomized Treatment Group

The definition of randomized treatment group, also known as the planned treatment group, will be the treatment group that a subject was randomized to. Placebo from each cohort will be pooled. The randomized treatment groups for summary purpose are: BIO89-100 3 mg QW, BIO89-100 9 mg QW, BIO89-100 18 mg QW, BIO89-100 27 mg QW, BIO89-100 18 mg Q2W, BIO89-100 36 mg Q2W, and Placebo.

[figure not shown]

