9.4.3.1. Responder Analysis

Responder analysis will be performed for MRI-PDFF. The proportion of subjects that reach a percentage reduction of ≥ 10 , ≥ 20 , ≥ 30 , ≥ 40 and ≥ 50 in MRI-PDFF will be summarized based on observed data at that visit. The following will be analyzed with a Fisher's Exact Test.

- Proportion of subjects who have ≥ 30 percent reduction in MRI-PDFF from baseline to Day 92.

- Proportion of subjects who have ≥ 30 percent reduction in MRI-PDFF from baseline to Day 50.
- Proportion of subjects who have MRI-PDFF $< 5\%$ at Day 92.
- Proportion of subjects who have MRI-PDFF $< 5\%$ at Day 50.

9.4.3.2. **Supportive Analysis**

Supportive analysis of MRI-PDFF will be performed: with sensitivity analysis to assess impact of missing data using multiple imputation using a pattern-mixture model (PMM) approach using control-based pattern imputation, correlation analysis and non-parametric analysis.

9.4.3.2.1. **Multiple Imputation Using Control Based Pattern-Mixture Model**

Multiple imputation will be performed using the placebo group to impute the missing values for the BIO89-100 subjects. This imputation will account for the possibility that not all data are missing at random. This method of multiple imputation assumes that the missing data post study discontinuation for BIO89-100 subjects are missing not at random (MNAR). By using the placebo subject data to impute the missing data from the BIO89-100 group, the analysis will produce a conservative estimate of the treatment effect of BIO89-100, although not as conservative as the worst observed case analysis.

Prior to applying the control-based pattern mixture, the first step will be to impute the non-monotone missing data assuming the missing at random (MAR) assumption. Only missing data that are sandwiched by two non-missing records in time will be imputed using the MAR assumption. Visit window mapping should also decrease the amount of non-monotone missing imputations that need to be done. After the non-monotone missing data patterns are filled in then the control-based imputation is applied.

| Missing Data Pattern | Baseline | D50 | D92 |
|----------------------|----------|-----|-----|
| Monotone | X | X | .b |
| Non-Monotone | X | .a | X |

.a is a missing value that will be imputed assuming the MAR assumption because it is sandwiched by two non-missing records; the earlier records will be imputed first.

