.b is a missing value that will be imputed assuming the NMAR assumption because it is monotone missing.

9.4.3.3. **Correlation Analysis**

Correlation analysis will be performed for MRI-PDFF and key liver biomarker data using the PD analysis set. The pairwise Pearson correlation will be calculated for each combination of MRI-PDFF, CAP score, VCTE score, ALT, AST, ELF Score, Pro-C3, triglycerides, LDL and HDL change from baseline within Day 50, within Day 92 and between Day 50 and Day 92 by treatment group (subjects on BIO89-100 only) and for pooled placebo.

9.4.3.4. **Non-Parametric Analysis**

Non-parametric analysis of the change from baseline and percent change from baseline to Day 50 and Day 92 for MRI-PDFF will be compared by treatment group and the p-value from the

Wilcoxon Rank Sum test will be presented. The Hodges-Lehmann estimate of location shift will be used to estimate the median and the exact 90% confidence limits.

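### The Part 1 multiple-imputation sample code pools treatment differences by visit alone, so as written it cannot give the dose-versus-pooled-placebo difference for MRI-PDFF

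*SAP*

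**What the plan says.** **Comparison.** Protocol section 8.4 says that the assessment of biomarker and pharmacodynamic endpoints "will employ 90% confidence intervals and significance testing for assessing within group changes", and also names "comparisons of the BIO89-100 doses to the pooled placebo group". SAP Part 1 section 3.5 frames its MRI-PDFF power assessment the same way: cohorts of 9, 12 and 14 subjects "compared to the pooled 19 placebo subjects will provide" a power that is redacted.

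**Groups.** SAP Part 1 section 5.10 states: "Placebo from each cohort will be pooled". Its list of seven summary groups ends with "BIO89-100 18 mg Q2W, BIO89-100 36 mg Q2W, and Placebo".

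**Visits.** In section 9.4.3.2.1 the header of the missing-data table reads "Missing Data Pattern | Baseline | D50 | D92", so there are two post-baseline MRI visits. That section describes the control-based imputation and says it gives a conservative estimate of the treatment effect. It does not say which contrast is estimated or how the differences are combined over imputations.

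**Code.** Section 13.1 requests 100 imputations. After imputation it fits the repeated-measures model and makes the same request as the main model code, "lsmeans trt*visit/pdiff cl", apart from a space and without the `alpha=0.1` option. It saves the arm means as `lsmeans` and the differences as `diffs`. The arm means are sorted and pooled by treatment and visit. The differences are sorted by visit and imputation, and PROC MIANALYZE is run on them by visit alone.

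**Intervals.** SAP section 9.1.2 asks for two-sided 90% and 95% intervals for the LS means and their differences.

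**The concern.** PROC MIANALYZE combines one estimate per imputation within each BY group, so each BY group must hold a single contrast. Here the BY variable is the visit of the first-listed cell only. The differences data set also carries the first treatment, the second treatment and the second visit, and the pooling step uses none of them. Every contrast that shares a first visit therefore lands in one group.

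The control-based imputation is the only missing-data sensitivity analysis for MRI-PDFF described in the visible text. Its purpose is to show whether the comparison with placebo survives a less favourable assumption about dropout. The step at fault is the one that would produce that comparison.

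**Working it through.** **1. The plan's own counts.** From SAP Part 1 Table 1, taking Cohorts 1 to 6 in order:
- Placebo: 2 + 3 + 4 + 3 + 4 + 3 = 19, as stated.
- Active: 6 + 12 + 14 + 9 + 14 + 9 = 64.
- Total: 64 + 19 = 83, as stated.

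The power figures cannot be reproduced because their inputs are redacted. The SAP gives no numerical figure for the imputation analysis.

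**2. Number of differences.** Seven groups at two visits give 7 × 2 = 14 cells. All pairs: 14 × 13 / 2 = 91 differences per imputation.

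**3. Differences wanted.** Six doses against placebo at the same visit, at two visits: 6 × 2 = 12. Share: 12 / 91 = 13%.

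**4. What each BY group holds.** List the cells by treatment and, within treatment, by visit, as the CLASS order in the code implies. A pair takes the visit of its first-listed cell.
- First cell at Day 50: 13 + 11 + 9 + 7 + 5 + 3 + 1 = 49.
- First cell at Day 92: 12 + 10 + 8 + 6 + 4 + 2 + 0 = 42.
- Same-visit pairs at either visit: 7 × 6 / 2 = 21, of which 6 involve placebo and 15 are dose versus dose.
- Cross-visit pairs: 49 − 21 = 28 and 42 − 21 = 21.

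| BY group | Rows per imputation | Dose vs placebo, same visit | Dose vs dose, same visit | Cross-visit | Rows over 100 imputations |
|---|---|---|---|---|---|
| Day 50 | 49 | 6 (12%) | 15 | 28 | 4,900 |
| Day 92 | 42 | 6 (14%) | 15 | 21 | 4,200 |

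A correctly formed contrast has 100 rows, one per imputation. No dose-versus-placebo contrast has a BY group of its own. The 49/42 split depends on the listing order. The 12 in 91, and the mixing of all 21 same-visit pairs within each visit, do not.

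**5. Would running one dose plus placebo cure it?** That leaves 4 cells and 4 × 3 / 2 = 6 differences per imputation. The Day 50 group holds 3 + 1 = 4 rows, 1 of them wanted. The Day 92 group holds 2 + 0 = 2 rows, 1 of them wanted. Cross-visit rows remain, so subsetting alone does not repair the step.

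**6. After correction.** Keeping same-visit rows with placebo as one member, pooled by dose and visit, leaves 12 contrasts of 100 rows each: 1,200 rows instead of 9,100.

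**The case against.** The strongest reply is that section 13.1 is labelled sample code and is plainly not a production program. It has a misspelled option (`niimpute`), two spellings of the imputation variable, a data set name that does not match the preceding output (`imputed` against `imputed1`), and no transposition back to long format. A programmer has to repair it before it runs, and the target comparison is clear from protocol 8.4 and SAP 5.10. The analysis is labelled supportive, the protocol calls the p-values on these endpoints descriptive, and there is no multiplicity adjustment. All of this stands and lowers the stakes. It does not remove the point: the SAP text names neither the contrast nor the pooling for this analysis, so the code is the only specification, and on this step it is wrong. The arm means in the same program carry the right identifiers.

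Some stronger readings are tempting but not supported.

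- **A reader might infer that the LSMEANS request is the error.** It is not. It produces labelled differences that include the wanted ones, and in the main repeated-measures output they can be read off directly. The fault is the later sort and pooling.
- **A reader might infer that no dose has a usable control-based estimate.** The imputed arm means are pooled by treatment and visit, so this fault leaves them untouched. Only the difference from placebo is lost.
- **A reader might infer that a diluted effect of some given size would be reported.** That would require SAS to average the repeated rows rather than stop, an assumed effect at every dose and visit, and a particular sort order; with placebo listed last instead of first, the sign reverses. The documents supply none of this.
- **A reader might infer that the rank-test sample code yields a seven-group omnibus test.** Section 9.4.3.4 says the changes "will be compared by treatment group and the p-value from the" Wilcoxon rank sum test, and adds a Hodges-Lehmann shift. Both are two-sample methods, and the input data set name is a placeholder. One dose plus placebo is the natural reading, so clearer wording there is optional.

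**Conclusion.** Wrong as written; minor. In the Part 1 SAP, the imputation code pools differences by visit alone. Of 91 differences per imputation, 12 are the comparison that protocol 8.4 calls for, 6 of 49 in the Day 50 group and 6 of 42 in the Day 92 group, and none is isolated. The control-based dose-versus-pooled-placebo difference, with its standard error, interval and p-value, is therefore not obtained.

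This rests on seven treatment levels, two MRI visits, 100 imputations and cells listed by treatment then visit. Whether SAS would stop or combine the repeated rows was not tested; neither outcome gives the planned estimate. The documents do not support any figure for bias in a reported result.

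**What to change.** In SAP Part 1 section 13.1, before PROC MIANALYZE is run on the differences:

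1. Keep only rows in which `visit` equals `_visit` and one of `trt` and `_trt` is placebo.
2. Orient every row as dose minus placebo. The imputation step identifies placebo as level 0; if `trt` is coded the same way, placebo is listed first and the raw differences are placebo minus dose, so their signs must be reversed.
3. Sort and pool by dose and visit, giving 12 contrasts with 100 rows each.
4. Output both the 90% and the 95% intervals, as section 9.1.2 requires. The imputation code sets no `alpha`, so only the default 95% limits would appear; replacing them with `alpha=0.1` alone would drop the 95% limits.

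Correct the option, variable and data set names in the same edit. Add one sentence to section 9.4.3.2.1 saying that the estimate is each dose minus pooled placebo at Day 50 and at Day 92.

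Optional clarification: state that the Wilcoxon, Hodges-Lehmann and Fisher analyses each use one dose plus pooled placebo at one visit.

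The cost is a few lines of code and text. No new data are needed.

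### The placebo-based imputation of missing MRI-PDFF scans leaves out baseline, which the analysis model adjusts for, and the SAP does not state the imputed scale (minor; free to fix)

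*SAP*

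**What the plan says.** SAP Part 1, section 9.4.3.2.1, sets out the method: "Multiple imputation will be performed using the placebo group to impute the missing values for the BIO89-100 subjects". The text describes the result as conservative and lists no variables for the imputation model. Its pattern table, headed "Missing Data Pattern | Baseline | D50 | D92", shows baseline observed in both foreseen patterns. Day 50 missing with Day 92 seen is filled first, under missing at random. Day 92 missing with Day 50 seen gets the placebo-based draw: "b is a missing value that will be imputed assuming the NMAR assumption because it is monotone missing".

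The imputation variables appear only in section 13.1, under "Sample SAS Code for Multiple Imputation Using Control Based Pattern-Mixture Model". Both PROC MI steps use "var trt01pn day50 day92". The second step has "monotone reg(/details" with no covariates named, and restricts the model to placebo subjects through "mnar model (day50 day92/modelobs=( trt01pn ='0". The analysis step is "model pchg = base trt visit trt *visit/ddfm=kr". Section 9.1.2 also puts baseline in the main MMRM.

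**The concern.** An imputation model should carry at least the variables that the analysis model conditions on. Here baseline is observed for the foreseen patterns and used in the analysis, but it has no part in generating the missing values.

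This is the only missing-not-at-random check stated for MRI-PDFF, and its stated purpose is a conservative estimate. Baseline is what separates a subject whose liver fat has fallen from one whose liver fat was always low. Without it, a placebo-based draw can give a BIO89-100 subject a larger reduction than the same method would give with baseline included. Whether this happens depends on the scale of day50 and day92, which the SAP leaves open.

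**Working it through.** **What the code does.** With no covariates named, each variable is regressed on those listed before it. The placebo restriction means that Day 92 is drawn from the placebo regression of day92 on day50, evaluated at the subject's own Day 50 value. Given Day 50, baseline adds nothing.

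**Plan's own figure.** There is none to reproduce. The MRI-PDFF effect size, SD and power in section 3.5 are redacted, and no result is stated for the imputation.

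**Assumed inputs (not from the documents).** Baseline PDFF mean 21, SD 7. Placebo percent change −5 at Day 50 and −8 at Day 92; BIO89-100 −50 and −55. SD of percent change 15 to 35 points at both visits. Day 50–Day 92 correlation ρ 0.5 to 0.9. Percent change independent of baseline. The simulations also hold baseline at 10 or above.

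**One subject, PDFF scale, SD 25, ρ = 0.7.** Take a BIO89-100 subject with Day 50 PDFF of 10%.

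- With baseline b, the placebo regression is D92 = b × (0.92 − 0.7 × 0.95) + 0.7 × D50 = 0.255b + 0.7 × D50.
- Without baseline, Var(D50) = 0.95² × 49 + 0.25² × (49 + 21²) = 44.22 + 30.63 = 74.85. Cov(D50, D92) = 0.95 × 0.92 × 49 + 0.7 × 0.25² × 490 = 42.83 + 21.44 = 64.26.
- The slope is 64.26 / 74.85 = 0.859. The intercept is 21 × 0.92 − 0.859 × 21 × 0.95 = 2.19. At D50 = 10 the expected Day 92 value is 10.8, whatever the baseline.

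| Baseline | Mean imputed change, no baseline | With baseline |
|---|---|---|
| 30% | 10.8/30 − 1 = −64% | 14.65/30 − 1 = −51% |
| 20% | 10.8/20 − 1 = −46% | 12.1/20 − 1 = −39.5% |
| 12% | 10.8/12 − 1 = −10% | 10.06/12 − 1 = −16% |

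Excluding baselines below 10 changes the middle column to −63, −45 and −8. The error runs both ways: subjects with a high baseline look better without it, subjects with a low baseline look worse.

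**Average over the BIO89-100 arm (Day 50 seen, Day 92 missing).** With baseline, the mean is −8 + ρ × (−50 + 5), which is −30.5, −39.5 and −48.5 for ρ = 0.5, 0.7 and 0.9. The simulated PDFF-scale means agree closely:

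| SD, ρ | No baseline | With baseline | Shift |
|---|---|---|---|
| 15, 0.5 | −45.9 | −30.5 | 15.4 |
| 25, 0.7 | −44.9 | −39.3 | 5.6 |
| 35, 0.9 | −47.7 | −47.0 | 0.7 |

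Across all nine settings the shift is about 1 to 15 points, always towards a larger reduction. If the variables are percent changes, the mean shift is about 0.

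**Treatment difference at trial size.** 14 active against 19 placebo (section 3.5), SD 25, ρ = 0.7, with an ANCOVA at Day 92 standing in for the MMRM, PDFF scale:

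| Active Day 92 scans missing | No baseline | With baseline | Shift |
|---|---|---|---|
| 1 of 14 | −45.8 | −45.4 | 0.4 |
| 2 of 14 | −45.7 | −44.9 | 0.8 |
| 3 of 14 | −44.6 | −43.5 | 1.1 |

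The SD of the estimate is 8 to 9 points. On the percent-change scale the two columns agree on average. Within a single simulated trial, the mean absolute gap is 0.8 to 1.8 points (PDFF) or 0.5 to 0.9 (percent change).

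**The case against.** The best defence is that the code is labelled as a sample and contains slips that show it was not run as printed: a misspelt option, and an input data set whose name does not match the preceding output. The method text could be read as intending baseline, since the pattern table has a column for it. This is also a supportive analysis of a secondary biomarker, with no multiplicity control and no formal hypotheses for the primary objectives. All of that bears on severity. It does not remove the gap, because no other place in the SAP names the imputation variables.

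The defence is also right that the effect depends on scale. The analysis variable is percent change, so day50 and day92 may be percent changes, and then omitting baseline costs almost nothing on average.

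A reader might go further in three ways that the documents do not support.

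- **That the imputed value is unrelated to the subject's own liver fat.** The placebo-based draw uses the subject's own Day 50 scan. In the simulations the imputed Day 92 value correlates 0.61 to 0.95 (PDFF) or 0.47 to 0.90 (percent change) with that scan. A subject with neither scan is outside the MRI analysis set (section 8.6), and early-termination scans are mapped to Day 50 or Day 92 (section 9.1.3). The remaining exception is a non-termination scan on Study Days 65 to 77, which falls in neither window.
- **That an imputed drop-out could count as a responder at the 30% threshold.** Sections 9.4.3 and 9.4.3.1 base those proportions on observed data, and the imputed data feed only the model for percent change.
- **That the analysis becomes anti-conservative outright.** The imputed PDFF-scale means without baseline, about −34 to −51, are still less favourable than the assumed active mean of −55. The conservatism is reduced, not reversed.

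**Conclusion.** The point holds as a mismatch between the imputation and analysis models, together with an unstated imputation scale. The variable lists, the missing-data patterns and the analysis set come from the SAP; every numerical effect rests on the assumed inputs above.

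On the PDFF scale, omitting baseline makes the check less conservative than the same method with baseline. The effect is sizeable for some individual imputed values, but small in the treatment difference relative to its sampling error. Minor severity: a free improvement, and no threat to the main MRI-PDFF conclusion.

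**What to change.** In both PROC MI steps of SAP Part 1 section 13.1, change the list to `var base trt01pn day50 day92`, with baseline ahead of day50 so that the monotone regressions use it. In section 9.4.3.2.1, add one sentence that names the imputation variables and states whether PDFF values or percent changes are imputed. If PDFF values are imputed, state that percent change is derived afterwards.

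The cost is one word in each of two code lines and one sentence of text. No extra data are needed, since baseline is already observed in the patterns the SAP foresees, and there is no evident downside.
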